6.2. Safety/Tolerability Population

All safety/tolerability analyses will be implemented using an intent-to-treat approach, which is defined as all subjects who are randomized and receive at least one dose of study medication.

7. PRIMARY ANALYSES

7.1. *Primary Objective #1: Evaluate the activity of Ibudilast (MN-166: 100 mg/day) versus placebo at 96 weeks as measured by quantitative MRI analysis for whole brain atrophy using brain parenchymal fraction (BPF).*

The first primary objective of the proposed study is to evaluate the activity of Ibudilast (MN-166) versus placebo by assessing the difference in rates of change in brain parenchymal fraction (BPF) between the Ibudilast and placebo treatment groups as measured at baseline, weeks 24, 48, and 96 post randomization. The evaluation of activity is defined as the test of the null hypothesis that the BPF rates of change in the treatment and placebo groups are equal.

The raw data will be summarized graphically, and in the following table:

Table 7.1: Descriptive statistics of BPF over time

Visit	Ibudilast	Placebo
Baseline		
Mean (SD)	x.xx (xx)	x.xx (xx)
Min. – max.	x.xx-x.xx	x.xx-x.xx
missing	xx	xx
Week 24		
Mean (SD)	x.xx (xx)	x.xx (xx)
Min. – max.	x.xx-x.xx	x.xx-x.xx
missing	xx	xx
Week 48		
Mean (SD)	x.xx (xx)	x.xx (xx)
Min. – max.	x.xx-x.xx	x.xx-x.xx
missing	xx	xx
Week 72		
Mean (SD)	x.xx (xx)	x.xx (xx)
Min. – max.	x.xx-x.xx	x.xx-x.xx
missing	xx	xx
Week 96		
Mean (SD)	x.xx (xx)	x.xx (xx)
Min. – max.	x.xx-x.xx	x.xx-x.xx
missing	xx	xx

The null hypothesis can be evaluated based on an assessment of parameter estimates from a linear mixed model (LMM: Laird and Ware, 1982). LMMs are advantageous for longitudinal clinical trials because they can account for dependency due to repeated measures with relatively few parameters, which potentially enhances statistical efficiency. Furthermore, LMMs can accommodate incomplete cases (i.e., missing data), which is expected in this study due to dropout. LMMs are typically estimated using maximum likelihood methods (Verbeke and Molenberghs, 2000) that yield valid inferences with incomplete cases under the widely applicable assumption that the missing data are ignorable (Little and Rubin, 2002).

For this analysis, assuming linear change over time, the LMM can be written in the following manner:

$$Y_{ij} = \alpha + \beta_1 x_{1i} + \beta_2 x_{2i} + \beta_3 t_{ij} x_{3i} + \beta_4 t_{ij} x_{4i} + a_i + b_i + \epsilon_{ij}$$

where:

- Y_{ij} is the BPF value for the j^{th} subject at the j^{th} time point
- α is the common intercept parameter
- t_{ij} denotes time (in weeks)
- $x_{1i} = 1$ if the subject was thought to be receiving immunomodulation therapy at randomization (IFN/GA), and 0 if the subject was not thought to be receiving immunomodulation therapy
- $x_{2i} = 1$ if the subject was thought to have primary progressive MS at randomization, and 0 if the subject was thought to have secondary progressive MS
- $x_{3i} = 1$ if the subject is in the treatment group
- $x_{4i} = 1$ if the subject is in the placebo group
- a_i and b_i are random effects (random intercepts and slopes)
- ϵ_{ij} is a random error term

After randomization, it is expected that a small number of enrolled subjects may be discovered to fall into a different stratum than that which was thought to be true at the actual time of randomization. For any such subjects, the true strata value discovered post-randomization (not the value thought to be true at the time of randomization) will be used for the models.

Assuming a common intercept constrains the baseline means to be equal, which controls for any initial imbalance that might occur due to empirical randomization (Senn, 2013). We make the typical assumptions:

$$\begin{bmatrix} a_i \\ b_i \end{bmatrix} \sim N(\mathbf{0}, \mathbf{G}), \quad \varepsilon_{ij} \sim N(0, \sigma^2 \mathbf{I}_i), \quad \text{and} \quad \begin{bmatrix} a_i \\ b_i \end{bmatrix} \perp \varepsilon_{ij}$$

In this model, the parameters β_1 and β_2 are included to adjust the model for the two stratification variables (immunomodulation therapy status at randomization & disease status at randomization). The main parameters of interest are β_3 and β_4 , which correspond to the estimated slopes in the treatment and placebo groups, respectively. The desired test of interest can be obtained by testing the null hypothesis of the following contrast:

$$H_0: \theta_1 = \beta_4 - \beta_3 = 0$$

against the alternative

$$H_1: \theta_1 \neq 0.$$

This null hypothesis can be evaluated with the likelihood ratio test, or a Z-test, provided a sufficiently large sample size which is provided in the proposed study. The Z statistic of interest is:

$$Z = \hat{\theta}_1 / SE(\hat{\theta}_1),$$

and leads to the rejection of H_0 when

$$|Z| < Z_{1-\alpha/2}$$

with the latter being the $100(1-\alpha/2)^{\text{th}}$ quartile of the standard normal distribution.

If we fail to reject H_0 , then we will conclude that there is no significant difference in the change of BPF between the treatment group and the placebo group over 2 years. If H_0 is rejected in favor of the alternative, and θ_1 is greater than zero, then we will conclude that the study provides evidence that the rate of BPF change is slower in the Ibudilast treatment group relative to the placebo group. However, if H_0 is rejected in favor of the alternative, and θ_1 is less than zero, then we will conclude that the study provides evidence that the rate of BPF change is faster in the Ibudilast treatment group relative to the placebo group. It is important to note that failure to reject the null hypothesis does not imply acceptance of the null hypothesis of no difference in slopes over time for the two groups.

The data from the fitted model will be summarized graphically, and in the following table:

Table 7.2: Estimated rate of BPF change by treatment group

Treatment group	Estimated rate of BPF change 90% CI	p-value for difference in rate of change
Ibudilast	xx (xx, xx)	0.xx
Placebo	xx (xx, xx)	

Since the longitudinal measurements will span up to five time points per participant (baseline, 24, 48,

72, and 96 weeks), there is a possibility that the BPF trajectories will not be linear. In order to assess the sensitivity of the results to the assumption of linearity, non-linear trends will be modeled by inserting time as a categorical variable. For this modelling approach, visits that were performed outside of an expected scheduled visit will be categorized into the next expected scheduled visit. We will compare model fit between the non-linear and linear models using the AIC, and will report results from the non-linear model if the AIC suggests that the nonlinear model provides a better fit. In this case, the primary comparison will involve a comparison of the estimated means of the two groups at each time point, and will be displayed in a table similar to the following:

Table 7.3: Model based estimates of BPF over time

Visit	Model Based		p-value for difference
	Ibutilast	Placebo	
Baseline Estimate (SE) 90% CI	xx (xx) (xx, xx)	xx (xx) (xx, xx)	0.xx
Week 24 Estimate (SE) 90% CI	xx (xx) (xx, xx)	xx (xx) (xx, xx)	0.xx
Week 48 Estimate (SE) 90% CI	xx (xx) (xx, xx)	xx (xx) (xx, xx)	0.xx
Week 72 Estimate (SE) 90% CI	xx (xx) (xx, xx)	xx (xx) (xx, xx)	0.xx
Week 96 Estimate (SE) 90% CI	xx (xx) (xx, xx)	xx (xx) (xx, xx)	0.xx

The residuals of the fitted statistical models will be examined for evidence of departure from assumptions, such as normality. If assumptions appear to be grossly violated, then transformations of response variables might be considered. It is also possible that some baseline characteristics will be imbalanced between the two treatment groups. In this case, the model may be expanded to include adjustments for the imbalanced characteristics. As specified in [section 6](#), the primary analysis will be conducted using a modified intent-to-treat analysis, which includes all subjects who are randomized, receive at least one dose of study medication, and have at least one efficacy assessment in the double-blind phase.

Finally, the proposed study involves multiple sites, which is a potential source of additional variation. Patients within a site tend to be correlated due to similarity of environment, e.g. because of testing by the same set of clinicians (Localio et al, 2001). Sensitivity analyses may also be conducted to account for site variation by augmenting the models described above with additional random effects and associated variance components.

7.2. Primary Objective #2: Evaluate the safety and tolerability of Ibutilast (MN-166) versus placebo

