Suppose Y_{ij} is the BPF value for the i th patient ($i = 1, \dots, N$) at the j th month ($j = 1, \dots, n_i$), t_{ij} denotes time in weeks, P stands for placebo, and T stands for treatment. Assuming linear change over time, the LMM can be written as the following,

$$Y_{ij} = \alpha_P + \beta_P t_{ij} + (\gamma + \delta t_{ij})g_i + (a_i + b_i + \epsilon_{ij}) \quad (1)$$

where g_i is a dummy variable for group,

$$g_i = \begin{cases} 0 & \text{if } P, \\ 1 & \text{if } T. \end{cases}$$

In Equation (1), α_P , β_P , γ , and δ are fixed effects; α_P is the intercept for the placebo group, β_P is the slope for the placebo group, $\gamma = \alpha_T - \alpha_P = 0$ is the difference of the intercepts, and $\delta = \beta_T - \beta_P$ is the difference of the slopes. Setting $\gamma = 0$ constrains the baseline means to be equal, which controls for initial imbalance that occurs in empirical randomization (Senn, 2013). The terms a_i and b_i are random effects (random intercepts and slopes, respectively), and ϵ_{ij} is random error. We make the typical assumptions

$$[a_i \ b_i]^T \sim \mathcal{N}(\mathbf{0}, \mathbf{G}), \epsilon_{ij} \sim \mathcal{N}(0, \sigma^2 \mathbf{I}_i), \text{ and } [a_i \ b_i]^T \perp \epsilon_{ij}.$$

The prime object of inference is δ , as this is the index of longitudinal activity of T versus P , namely, the difference in rates of change. The null hypothesis of no longitudinal ibudilast effect (equality of T and P slopes) is $H_0: \delta = 0$, and can be evaluated with the likelihood ratio test, or a Z -test, provided a sufficiently large sample size that is provided in the proposed study ($N = 250$, see Sample Size Justification below). The Z statistic is $Z = \hat{\delta}/SE(\hat{\delta})$ and leads to the rejection of H_0 when $|Z| > Z_{1-\alpha}$, with the latter value being the $100 \cdot (1 - \alpha)$ th quartile of the standard normal distribution (single-tailed test).

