8. SECONDARY ANALYSES

The major secondary objective of the SPRINT-MS study is to measure activity of Ibudilast at 96 weeks versus placebo using a variety of additional imaging metrics. Four separate imaging metrics will be considered.

- Diffusion tensor imaging (DTI) in descending pyramidal white matter tracts
- Magnetization transfer ratio (MTR) imaging in normal-appearing brain tissue
- Retinal nerve fiber layer as measured by optical coherence tomography (OCT)
- Cortical atrophy as measured by cortical longitudinal atrophy detection algorithm

8.1. Major Secondary Objective (a): *Evaluate the activity of Ibudilast (MN-166) versus placebo as measured by diffusion tensor imaging (DTI) in pyramidal white matter tracts.*

For both DTI outcomes of interest [Axial Diffusivity (LD), Radial Diffusivity (TD)], the comparison of outcomes for subjects on MN-166 versus placebo will be analyzed using a model similar to the described in [section 7.1](#) for the primary objective, with the exception that the outcome variable will be modified to represent the corresponding DTI outcome of interest and the model will include an additional random effect to account for measurements taken on both sides within the same subject.

8.2. Major Secondary Objective (b): *Evaluate the activity of Ibudilast (MN-166) versus placebo as measured by magnetization transfer ratio (MTR) imaging in normal appearing brain tissue.*

Because both MTR outcome measures of interest [Median MTR in normal appearing brain tissue (NABT) and Median MTR in normal appearing grey matter (NAGM)] record the values at each of the time points as the change from baseline, the LMM used to address this objective will be slightly modified from that described in [section 7.1](#). Assuming linear change over time, the LMM can be

written in the following manner:

$$Y_{ij} = \alpha + \beta_0 x_{0i} + \beta_1 x_{1i} + \beta_2 x_{2i} + \beta_3 t_{ij} x_{3i} + \beta_4 t_{ij} x_{4i} + a_i + b_i + \epsilon_{ij}$$

where:

- Y_{ij} is the change in the MTR value from baseline for the i^{th} subject at the j^{th} time point
- x_{1i} = the baseline MTR value for the i^{th} subject

and all other variables are defined in the same manner as described for the model in [section 7.1](#). The major secondary hypothesis of interest will involve a comparison of the β_3 and β_4 parameters, and will proceed in the same manner as described for the model in [section 7.1](#).

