The analysis used the proposed time points of 0, 24, 48, 72, and 96 weeks. Power curves were computed for DS1, DS2, and for their average (Avg). Avg was based on averaging the LMM parameter estimates across the data sets (e.g., average slope = [DS1 slope + DS2 slope] / 2). Avg was an attempt to pool information from the two data sets without the raw data (the raw data for DS2 was unavailable). A 10% dropout rate was assumed and all estimated sample sizes were inflated by this percentage (i.e., final sample size = initial sample size \times 1.10). Given the resources required for obtaining and analyzing 3T scans, the type I error rate was set at $\alpha = 0.10$. Figure 7.1 shows power curves for the three smallest effect sizes (30%, 35%, and 40%). Focusing on Avg for the middle effect size (35%), the figure indicates that a single-arm $N / 2 = 125$ provides close to 80% (power = 0.80 is the horizontal dashed line). The middle effect size is important as it nearly corresponds to the upper effect size of the aforementioned Ibudilast study (effect size = 36%). The Avg data source is preferred because it approximates a pooling of the information from both samples. The feasibility of $N / 2 = 125$ as the single-arm sample size was examined by calculating power for effect sizes with $\alpha = 0.10$ for all three data sources (DS1, DS2, Avg). The power by effect size curve and data source is shown in Figure 7.2. The figure clearly shows that the study has adequate power across the range of possible values suggested by these two data sources. For the “best” data (DS1), our study has slightly less than 90% power to detect effects of approximately 40% or larger, and more than 90% power to detect effects on the upper end of the range of interest (50%). Most importantly, the figure shows that the power based on the Avg data source is very high for effects in the 33% - 36% range of greatest interest (approximately 80% - 85%). Therefore, based on these assumptions, we are confident that a per-arm sample size of $N / 2 = 125$ ($N = 250$ total participants) is sufficient to help ensure statistically reliable results for the proposed study.

Figure 9.1: Power as a Function of Single-arm sample size, effect size, and data set

[figure not shown]
[figure not shown]

Figure 9.2: Power as a Function of Effect Size and data source for sample size of 125 and alpha = 0.10

9.2. Primary Objective #2: Evaluate the safety and tolerability of Ibudilast (MN-166) versus placebo

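### The primary BPF model is misprinted: the random slope b_i lacks its time factor in SAP 7.1, protocol Equation (1) and SAP 8.2, so the formula contradicts its own definition and the powered model

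*Combined protocol and SAP*

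**What the plan says.** SAP 7.1 prints the end of the primary model as "\beta_4 t_{ij} x_{4i} + a_i + b_i + \epsilon_{ij". The definitions below it say that a_i and b_i "are random effects (random intercepts and slopes") and give them a joint normal distribution with covariance G. Protocol 12.1.2, Equation (1), closes the same way, with "a_i + b_i + \epsilon_{ij", and says that the two terms "are random effects (random intercepts and slopes, respectively"). The MTR model in SAP 8.2 repeats the form. SAP 8.1, 8.3 and 8.4 take their models from 7.1.

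Other equations carry the time factor. The protocol's model with site effects multiplies the patient slope by time, and so does the OCT model (protocol 12.1.3, SAP 9.5). The power sections (protocol 12.1.3, SAP 9.1) build the random-effects design matrix Z_i from the columns 1 and t_ij.

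On timing, the opening sentence of SAP 7.1 describes BPF "as measured at baseline, weeks 24, 48, and 96 post randomization". SAP 9.1 states: "The analysis used the proposed time points of 0, 24, 48, 72, and 96 weeks".

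In SAP 8.2, x_1i is redefined as "the baseline MTR value for the" subject. In SAP 7.1, x_1i is the IFN/GA indicator. The 8.2 equation also contains an x_0i that is never defined.

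**The concern.** The quantity tested is a difference in mean slopes. Its standard error must reflect two sources of variation: scan-to-scan error, and real differences between patients in how fast their brains shrink. The second enters only through the random slope. With no t_ij on b_i, the printed formula has two random intercepts that cannot be told apart and no term for patients' differing slopes.

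An analyst who fits a random intercept alone pushes slope differences into the residual, where they are treated as independent noise. The standard error is then too small and the declared 0.10 level is not held. The interim efficacy test uses the same endpoint and would be affected too.

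A primary model should be programmable without a choice. Here the formula and its definitions lead to different models with materially different p-values. The protocol adds to this by planning to revert to Equation (1) if site variance is negligible, which on paper moves from a model that prints the random slope to one that does not.

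**Working it through.** **The plan's own figure.** SAP 9.1 gives power close to 80% for a 35% slope reduction with 125 per arm and alpha 0.10. This cannot be reproduced, because the pilot slope, G and σ² are not printed. Its anchors roughly agree with each other. Under power = Φ(c × effect − 1.645), 80% at 35% gives c = (1.645 + 0.842)/0.35 = 7.10, hence 76% at 33% and 82% at 36%. The plan states about 80% to 85% for that range.

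**What the printed formula means.** With random part a_i + b_i, every pair of visits has the same covariance, Var(a_i + b_i). Only that sum can be estimated, so the three elements of G cannot be separated. The powered model has V = Z G Zᵀ + σ²I with Z = (1, t), which is a different covariance.

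**Effect on the standard error if coded literally.** Let s² be the residual variance, sb² the slope variance and Sxx the sum of squared time deviations. For scans at 0, 24, 48, 72 and 96 weeks (mean 48), Sxx = 48² + 24² + 0 + 24² + 48² = 5760.

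- True variance of one patient's slope: s²/Sxx + sb².
- Random intercept only: five scans leave 4 within-patient degrees of freedom, so the residual mean square has expectation s² + sb²·Sxx/4. Dividing by Sxx gives s²/Sxx + sb²/4.
- With r = sb²/(s²/Sxx), the ratio of reported to true SE is k = √[(1 + r/4)/(1 + r)].
- Two-sided type I error at nominal 0.10 (the SAP's two-sided alternative) is 2Φ(−1.645k).

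The share of slope variance due to real slope differences, r/(1 + r), is an assumption:

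| Share | r | k | 1.645k | Type I error |
|---|---|---|---|---|
| 20% | 0.25 | 0.92 | 1.52 | 13% |
| 50% | 1 | 0.79 | 1.30 | 19% |
| 80% | 4 | 0.63 | 1.04 | 30% |
| near 100% | very large | 0.50 | 0.82 | 41% |

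At the interim, nominal p = 0.0104 corresponds to z = 2.56. With k = 0.79 the effective z is 2.02, a false-positive rate of about 4%.

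**Simulation check.** This used 250 patients, five scans and 4,000 runs, with assumed residual SD (% of BPF) and slope SD (% per year). The printed form rejected a true null in 18.7% (0.2 and 0.137), 36.5% (0.2 and 0.5) and 21.8% (0.4 and 0.3) of runs. With the random slope fitted, rejection was 9.6% to 10.7%.

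**Variances tied to the stated power.** The slope SD was solved to give 80% power at a 35% effect. The placebo slope was 0.5, 1.0 or 1.5% per year (the range quoted in SAP 2.1). The residual SD was 0.1% to 0.4%, around the scan-rescan figure of under 0.2% in SAP 2.1. Intercept SD was assumed to be 4% with zero correlation, and n was 125 or 125/1.10 ≈ 114 per arm. The SE ratio was 0.49 to 0.67 and type I error 0.27 to 0.42. This calculation uses the common-intercept model, so its lower end falls just below the closed-form bound of 0.50.

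**Week 72.** Without it, the times 0, 24, 48 and 96 have mean 42, and Sxx = 42² + 18² + 6² + 54² = 5040. If there is no slope variation, the SE rises by √(5760/5040) = 1.069, and 80% power becomes Φ(2.487/1.069 − 1.645) = 75%. At r = 1 the variance goes from 2 to 1 + 5760/5040 = 2.143, the SE rises by 3.5%, and power becomes 78%. In the scenarios tied to the stated power, the SE rises by 0% to 1.9% and power is 0.787 to 0.800.

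**The case against.** The strongest reply is that the documents already show which model is meant. The definitions say slopes, G is a joint covariance for both terms, and SAP 9.1 presents its random-slope matrix form as the model of section 7.1. Nobody chose a random-intercept analysis. Because the literal formula cannot be estimated with a two-by-two G, a programmer would probably go back to the definition and find the word slope. This stands. A reader might infer that the plan has no random slope, or that the trial was powered for a model it will not use. The documents do not support either reading.

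A reader might also infer that the short visit list in SAP 7.1 adds to the understated standard error, or that Week 72 scans will be discarded. Neither follows. Losing a visit widens the standard error, and Week 72 appears in SAP 2.1, the mITT definition in 6.1.1, Tables 7.1 and 7.3, the five-time-point statement in 7.1, and SAP 9.1. The two harms cannot both be at their worst either: 41% type I error needs slope variation to dominate, where a lost visit costs almost nothing, and 75% power needs none, where type I error stays at 10%.

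What the reply does not remove is the error in the operative formula. Loss in file conversion is an unlikely explanation, since the same factor is missing from three equations in two documents while other equations keep it.

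**Conclusion.** The point holds as a misprint in the primary-analysis equation, repeated in protocol Equation (1) and SAP 8.2. The formula is wrong as written, while the intended and powered model is sound. Harm arises only if the formula is coded against its stated definition. The SE would then be 0.92 to 0.50 of its true value, and type I error about 13% to 41% instead of 10%, for slope variation of 20% to nearly 100% of per-patient slope variance. Those shares are assumptions, so the result is a range and not a forecast.

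The Week 72 omission is a one-sentence slip that would raise the SE by at most about 7%. The x_0i/x_1i slip is a labelling error on a secondary endpoint; followed literally, it would drop the IFN/GA stratification covariate from the MTR model. None of this calls for a design change, and it does not rank with defects that would.

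**What to change.** - In SAP 7.1, SAP 8.2 and protocol Equation (1), print the random part as `a_i + b_i t_ij + ε_ij`. The covariance G already stated then applies as intended, and the models in SAP 8.1, 8.3 and 8.4 inherit the correction.
- In the opening sentence of SAP 7.1, list baseline and weeks 24, 48, 72 and 96.
- In SAP 8.2, define x_0i as baseline MTR and leave x_1i as the IFN/GA indicator.

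The cost is wording in two documents. Sample size, alpha, visits and budget are unchanged. The corrections should be made before the interim analysis, or at the latest before database lock, so that the model is not settled with results in view.

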All imaging endpoints will be statistically evaluated using linear mixed models (LMMs: Laird and Ware 1982). LMMs are advantageous for longitudinal clinical trials because they can account for the dependency due to repeated measures with relatively few parameters, which potentially enhances statistical efficiency. Furthermore, LMMs can accommodate incomplete cases (ie, missing data), which is expected in this study due to dropout. LMMs are typically estimated using maximum likelihood methods (Verbeke and Molenberghs 2000) that yield valid inferences with incomplete cases under the widely applicable assumption that the missing data are ignorable (Little and Rubin 2002). For all analyses, the residuals of the fitted statistical models will be examined for evidence of departure from assumptions, such as normality. If assumptions appear to be grossly violated, then transformations of response variables might be considered. Alternatively, generalized LMMs might be used because of their ability to accommodate a wider range of distributional forms (eg, beta distribution). The primary analysis will be conducted using a modified intent-to-treat analysis, which includes all subjects who are randomized and receive at least one dose of study medication in the double-blind phase. Since this is a phase 2 proof of concept study, statistical significance will be determined by any test that exceeds the 0.10 significance level. To account for baseline imbalance due to randomization vagaries, the baseline group means (intercepts) in the statistical analysis will be constrained to be equal. Sensitivity analyses will be conducted using brain atrophy as measured by SIENA and covariate adjustment for covariates with potential impact on atrophy (ie, non-steroidal anti-inflammatory drugs [NSAIDs]) that were unbalanced between treatment groups.

Safety Analysis:

The safety analyses will be conducted using the double-blind safety population, defined as subjects who are randomized and receive at least one dose of study medication in the double-blind phase.

Adverse events (AEs), discontinuation due to AEs, and serious adverse events (SAE) will be summarized by presenting, for each treatment group, the number and percentage of subjects with any AE, and AEs by system organ class and preferred term. Adverse events will be further summarized by severity and by relationship to study drug. The summary will be limited to treatment-emergent AEs.

Sample Size Justification:

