10. ASSESSMENT OF ACTIVITY

10.1. Primary and Secondary Endpoints

The primary endpoint is:

- Covariate-adjusted mean rate of change in brain atrophy over 96 weeks as measured by brain parenchymal fraction (BPF).

The following major secondary endpoints will be evaluated at 96 weeks:

- Diffusion tensor imaging (DTI) in descending pyramidal white matter tracts
- Magnetization transfer ratio (MTR) imaging in normal-appearing brain tissue
- Retinal nerve fiber layer as measured by Optical coherence tomography (OCT)
- Cortical atrophy as measured by cortical longitudinal atrophy detection algorithm [CLADA]

The additional secondary outcomes are to measure the activity of ibudilast (MN-166) at 96 weeks versus placebo on:

- Inflammatory disease activity, as measured by T1 lesion volume, T2 lesion volume, and annualized relapse rate
- Disability, as measured by Expanded Disability Status Scale (EDSS) and Multiple Sclerosis Functional Composite (MSFC)
- Quality of Life, as measured by Multiple Sclerosis Impact Scale (MSIS-29), EuroQol 5 Dimensions (EQ-5D), and Short Form-36 Health Survey (SF-36)
- Cognitive impairment, as measured by Symbol Digit Modalities Test and the Selective Reminding Test
- Neuropathic pain, as measured by Brief Pain Inventory (BPI).

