5. PRELIMINARY TABULATIONS

All subjects who provide informed consent will be accounted for in this study. Regularly generated enrollment reports will describe:

- Number of subjects consented, eligible, and randomized by site
- Ongoing study status of all randomized subjects
- Reasons for ineligibility
- Protocol deviations
- Early drug withdrawals
- Early study terminations

Subject data will also be summarized by treatment group (MN-166 vs. placebo) with respect to important demographic characteristics. Distribution of categorical variables will be tabulated by treatment group. Continuous variables will be summarized as mean, median, standard deviation, minimum, and maximum by treatment group and overall. Variables to be collected will include:

- Gender
- Race
- Ethnicity
- Age
- Participation in lumbar puncture study
- T2 lesion volume (CCs) at screening

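### SAP 7.1 adjusts the BPF level, but not the tested slope, for the two randomization strata: no bias, and a small, nearly free gain left untaken

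*Combined protocol and SAP*

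**What the plan says.** Randomization is 1:1 in permuted blocks within strata defined by immunomodulating therapy (IFN/GA or none) and disease type (PPMS or SPMS) (SAP 4). The protocol's primary endpoint is the "Covariate-adjusted mean rate of change in brain atrophy over 96 weeks" (protocol 10.1).

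The SAP 7.1 model has a common intercept, beta_1 times the IFN/GA indicator, beta_2 times the PPMS indicator, beta_3 times time in the ibudilast arm, beta_4 times time in the placebo arm, and random terms. Beta_1 and beta_2 "are included to adjust the model for the two stratification variables". The parameters of interest are beta_3 and beta_4, "which correspond to the estimated slopes in the treatment and placebo groups, respectively". The test is two-sided on theta_1 = beta_4 - beta_3 at alpha 0.10, and Table 7.2 is to show the "Estimated rate of BPF change by treatment group".

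On chance imbalance, SAP 7.1 adds that "the model may be expanded to include adjustments for the imbalanced characteristics". The protocol synopsis, under Endpoint Analysis, lists as a sensitivity analysis "covariate adjustment for covariates with potential impact on atrophy" for those "that were unbalanced between treatment groups".

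**The concern.** The strata enter the model for the level of BPF and stay out of the model for its slope, but the slope is what is tested. Stratified blocks balance the arms within each stratum, so any slope difference between strata largely cancels from the treatment contrast. A model without stratum-by-time terms does not recognise this. It leaves that variation in the random-slope variance and reports a standard error that is somewhat too large. At stake is a little power, plus agreement between the analysis and the way patients were randomized.

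Three smaller matters sit in the same text:

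- SAP 7.1 does not say whether a model expanded for imbalance would replace the primary one.
- Protocol Eq. (1), SAP 7.1 and SAP 8.2 print the random slope b_i without multiplying it by time.
- SAP 8.2 attaches baseline MTR to x_1i, although x_1i is the IFN/GA indicator in SAP 7.1 and the SAP 8.2 equation carries an x_0i that is not defined.

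**Working it through.** **Calibration.** SAP 9.1 states power close to 80% for a 35% slope reduction with 125 per arm, alpha 0.10 and sample sizes inflated by 1.10 for dropout. This cannot be reproduced independently: the pilot slope, G and sigma^2 are not printed, and the power curves are not visible in the text available. I therefore solve for the per-patient slope variance V that it implies, with B the placebo slope:

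- evaluable n = 125/1.10 = 113.6 per arm
- z values: 1.645 (two-sided 0.10) and 0.842 (power 0.80), sum 2.486
- V = 0.35^2 x 113.6 / (2 x 2.486^2) = 1.126 B^2, so the SD is 1.061 B

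**Assumptions.** D is the slope difference between the two levels of a factor, as a share of B, taken as equal for both factors. p is the share of patients in the smaller level, 0.2 to 0.5. The two factors are independent. The documents give neither D nor p.

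**Formulas.**

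- Share of slope variance lying between strata: r = 2p(1-p)D^2 / 1.126
- Type I error as planned: 2[1 - Phi(1.645/sqrt(1-r))]
- Power as planned: Phi(0.842/sqrt(1-r))
- Power with stratum-by-time terms: Phi(2.486/sqrt(1-r) - 1.645)

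| D | p | r | Type I error as planned | Power as planned | Power with time terms | Loss (points) |
|---|---|---|---|---|---|---|
| 10% | 0.2 | 0.0028 | 0.0995 | 80.03% | 80.10% | 0.07 |
| 10% | 0.5 | 0.0044 | 0.0992 | 80.05% | 80.15% | 0.10 |
| 20% | 0.2 | 0.0114 | 0.0981 | 80.13% | 80.40% | 0.26 |
| 20% | 0.5 | 0.0178 | 0.0970 | 80.21% | 80.62% | 0.41 |
| 30% | 0.2 | 0.0256 | 0.0957 | 80.31% | 80.90% | 0.59 |
| 30% | 0.5 | 0.0400 | 0.0932 | 80.48% | 81.40% | 0.92 |
| 50% | 0.2 | 0.0711 | 0.0879 | 80.87% | 82.51% | 1.64 |
| 50% | 0.5 | 0.1110 | 0.0811 | 81.40% | 83.95% | 2.55 |

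Losses are taken before rounding.

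**Simulation check.** Generalised least squares with known variances, 4,000 trials per setting, 114 per arm, permuted blocks in four strata, p = 0.5, both factors active, true effect 0.35 B:

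- Mean estimated effect: 0.347 B to 0.350 B for both models at D = 20% and 50%, so there is no bias.
- Power at D = 20%: 80.5% as planned, 80.9% with time terms.
- Power at D = 50%: 81.3% as planned, 83.8% with time terms.
- Type I error at D = 50%: 0.079 as planned, 0.100 with time terms.

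**Residual imbalance.** If one factor still differed by 5 percentage points between arms, the contrast would shift by 0.05 x D: 0.01 B at D = 20% and 0.025 B at D = 50%, against a target of 0.35 B.

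**Why centre.** With uncentred indicators, beta_3 and beta_4 become slopes in the reference stratum. At p = 0.5 and D = 50%, each factor moves them by p x D = 25% of B, and Table 7.2 would no longer show average group slopes. In 600 simulated trials with one such factor and a placebo slope of -0.50, beta_4 averaged -0.503 without time terms, -0.627 with uncentred terms and -0.503 with centred terms. Theta_1 was -0.178 in all three.

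**The case against.** The strongest reply is that pre-specified level terms for stratification factors are a legitimate choice, the contrast is unbiased, the error is on the safe side, and the gain rests on slope differences that the documents do not give. This largely stands. SAP 2.1 describes PPMS and SPMS atrophy as similar. The 30% to 50% treatment effects it cites are mainly for RRMS therapies, and the synopsis says no therapy has shown efficacy in progressive MS without relapses. A large D is therefore not what the documents lead one to expect for either factor. What remains is that the change costs almost nothing.

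A reader might infer more, in four ways that the documents do not support:

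- *The endpoint's covariate-adjusted wording promises stratum-by-time terms.* The protocol's own Eq. (1) has no stratum terms at all, so SAP 7.1 already adjusts more than the protocol model does.
- *The imbalance clause lets the primary result be selected and inflates type I error.* SAP 7.1 gives no trigger, no covariate list and no form (level or slope), so a rate of triggering or an inflation figure would rest on invented rules. The variables in SAP 5 are for describing the arms "with respect to important demographic characteristics" and are not called triggers. The synopsis puts such adjustment under sensitivity analyses. What is missing is a statement of status.
- *The printed b_i means no random slope is fitted.* SAP 7.1 names random slopes and gives them a two-dimensional covariance G, Z_i in SAP 9.1 includes the time column, and the protocol's site model multiplies the slope by time. It is a misprint.
- *The MTR model drops IFN/GA use.* SAP 8.2 says all other variables are defined as in SAP 7.1, so the intended meaning can be recovered. The label still needs correcting.

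**Conclusion.** The point holds as a small improvement. The tested slope contrast is not adjusted for the two factors used to randomize. The result is a valid, unbiased and slightly conservative test. With both factors active, the loss runs from under about 0.1 power points (D = 10%) to about 2.5 (D = 50%, p = 0.5), with type I error between about 0.099 and 0.081 against a nominal 0.10. These figures rest on the assumed D and p, equal and independent effects of the two factors, and the variance implied by the SAP's own statement of close to 80% power. The documents point towards the low end. Nothing here shows a stated power, sample size or significance level to be wrong. The imbalance clause needs one clarifying sentence, and the symbol and label points are errata.

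**What to change.** - **Primary model (SAP 7.1).** Add t_ij times the mean-centred IFN/GA indicator and t_ij times the mean-centred PPMS indicator. Beta_3 and beta_4 remain average group slopes for Table 7.2, and theta_1 is the common adjusted slope difference. Use the same model for the interim efficacy and futility assessment (SAP 11.2) and carry both terms into the secondary imaging models of SAP 8.
- **Imbalance clause (SAP 7.1).** State that expansion for observed baseline imbalance is a sensitivity analysis, as in the synopsis, and does not replace the primary model.
- **Errata.** Print b_i*t_ij in protocol Eq. (1), SAP 7.1 and SAP 8.2. In SAP 8.2, label baseline MTR x_0i so that x_1i is again IFN/GA use.

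The cost is SAP wording, settled before any unblinded analysis, and two fixed-effect parameters with about 250 patients. No new data are needed. Protocol section 12 leaves the detailed methods to the SAP, but Eq. (1) has no stratum terms, so the SAP should say that its model is the operative one. Correcting Eq. (1) itself needs the written approvals in protocol 16.1 (Steering Committee, NINDS, DSMB, CIRB) and can wait for the next amendment.
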